The second element was a weekly healthy food incentive of CDN\$10.50 per household member for 12 months. Participants earned the weekly incentive by purchasing whole, minimally processed foods with little to no added fat, sugar, or salt from all food groups in study-affiliated supermarkets, which were part of a large chain with multiple banners and locations.^{8, 39} Incentive-eligible foods included dairy products; whole grain bread, pasta, and cereal; fresh, frozen, and canned vegetables; fresh and frozen fruit; fresh, plain meats, fish, and poultry; canned fish and meat alternatives (eggs, canned and dried beans, plain almonds). Researchers calculated incentive amounts based on total household size as reported at baseline (0 months), which was communicated to participants after randomization. Once participants reached their spending threshold as defined by their household size, they immediately received loyalty card points equal to their eligible spending (e.g., a two-person household spending CDN\$21 received CDN\$21 in points). The incentive was capped at CDN\$10.50 per person per week, and points were only given to households that met or exceeded their threshold each week. Although progress towards meeting the minimum spend was reset weekly, earned points carried over between weeks, did not expire, and could be redeemed for anything in-store in CDN\$10 increments. However, participants were encouraged to use these points to continue the earn-reward cycle by purchasing incentive-eligible foods. At baseline, participants' loyalty cards were preloaded with points equivalent to one week's incentive amount to allow initial participation without paying out-of-pocket. The incentive redemption mechanism was pilot tested⁴⁰ and is fully described elsewhere.³²

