4.5 Baseline Characteristics

At baseline, we collected data on blocking variables (i.e., gender identity, recruitment location, A1C), and sociodemographic and health-related characteristics including date of birth, sex at birth, race/ethnicity and Indigenous identity, Canadian citizenship², years lived in Canada, postal code*, home ownership, marital status, household size and composition, household changes*, relocation during the FoodRx program*, educational attainment, education location*, annual household income, main income source, participation in income support programs, access to extended health benefits, employment status, smoking status, duration of diabetes, and number of household members with T2DM with space to identify the member (e.g., daughter).

5. Outcomes

This section is comprised of outcome descriptions including definitions, variable types, measurement, scoring, and cut points as applicable for each outcome. Non-RCT outcomes included in Section 7 are also described herein. All statistical models are described in Section 7.

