5.2.4 Patient Reported Outcomes

Household Food Insecurity

Household food insecurity, defined as inadequate or insecure access to food due to financial constraints,⁷⁹ was assessed using Health Canada's validated 18-item Household Food Security Survey Module (HFSSM).⁸⁰ We slightly modified the module to fit the study's data collection schedule. Response options were preserved in their original format, with the sole modification being a change in the reference period from 12 months to 6 months. Participants rated the frequency in which they 1) worried about running out of food for themselves and/or household members including children, 2) cut the size of their meals or skipped meals, and/or 3) went entire days without eating because there was not enough money for food. Response values range from 1 (never true) to 3 (often true) for primary questions, and 1 (only 1 or 2 weeks) to 3 (almost every week) for sub questions. Adults with children <18 years of age living in the home completed all 18 module questions. Adults with no children living in the home completed the 10 questions for adults only. Scoring is determined by the total number of affirmative responses, which are subsequently classified as food secure, marginally food insecure, moderately food insecure, or severely food insecure as described in Table 1.

We will assess the presence of household food insecurity as a binary variable by comparing those who were experiencing food insecurity (≥ 1 affirmative responses) to those who were food secure (0 affirmative responses). We will also assess the severity of household food insecurity as an ordinal variable by comparing those who experienced marginal, moderate, or severe food insecurity to those who were food secure.

Status	Interpretation	10 item adult food security scale	8 item child food security scale
Food secure	No report of income-related problems of food access.	No items affirmed	No items affirmed
Marginally food insecure	Some indication of worry or an income-related barrier to adequate, secure food access	Affirmed no more than 1 item on either scale	
Moderately food insecure	Compromise in quality and/or quantity of food consumed by adults and/or children due to a lack of money for food.	2 to 5 affirmative responses	2 to 4 affirmative responses
Severely food insecure	Disrupted eating patterns and reduced food intake among adults and/or children	6 or more affirmative responses	5 or more affirmative responses

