5.4.1 Incentive Usage

Incentive usage will be assessed as a count of the number of weeks participants earned the incentive and/or redeemed the incentive. The total possible weeks for both earning and redeeming the incentive is 52 weeks.

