7.2 Covariate Adjustments, Subgroup Analyses, and Sensitivity Analyses

Models will be adjusted for baseline values of each outcome, blocking variables, and covariates specific to each outcome, which are described in the manuscript sections.

Subgroup analyses will be conducted for one outcome in each paper. These analyses are described in each manuscript section.

We will conduct per protocol sensitivity analyses for each outcome wherein data for participants who did not adhere to their assigned group will be removed from the analysis. We will also conduct as-treated sensitivity analyses for each outcome wherein participants will be analyzed based on their incentive usage by 1) using pre-specified cut points based on percentage of incentives redeemed (25%, 50%, 75%), 2) basing usage on weeks used wherein participants who earned the incentive ≥ 27 weeks will be analyzed as part of the FoodRx group and participants who earned the incentive ≤ 26 weeks will be analyzed as part of the comparison group, and 3) basing usage on incentive level by comparing single households to the remaining levels (i.e., 2+ households and above). Additional sensitivity analyses are described in each manuscript section.

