7.4 Primary Manuscript

This paper will report results for 12-month A1C, our primary outcome, along with secondary and exploratory outcomes at 6-, 12-, and/or 18-months, including blood glucose levels, clinical health markers, and need for antihyperglycemic medication.

12-month A1C, Primary Outcome

We will assess the intention to treat effect of group assignment on mean A1C at 12-months as a continuous outcome using mixed-effects linear regression. The primary test will be the group \times time interaction contrast at 12-months (i.e., post-intervention), which estimates between-group differences in mean A1C from baseline to 12 months. Models will be adjusted for baseline A1C to estimate treatment effect while holding baseline A1C constant, and additional blocking variables (gender, recruitment location). To improve the precision of effect estimates, models will also be adjusted for age, race/ethnicity, educational attainment, number of children living in the home, and diabetes duration. Additionally, all models will include a data source indicator variable (study measured vs administrative health data), group (FoodRx vs comparison), collection timing (number of days measurement was taken since baseline), and restart cohort indicator variable (did not restart vs did restart). We will include random intercepts for participants (participant study ID) to account for within-subject correlation due to repeated measures, and for primary care clinics (clinic study ID) to account for clustering of participants within clinics. Missing data for covariates will be addressed using full information maximum likelihood.

We will conduct subgroup analyses for 12-month A1C by baseline household food insecurity severity (marginal, moderate, severe), gender (man, woman, gender diverse), recruitment location (urban setting, rural setting, Indigenous primary care clinic), Indigenous identity, baseline A1C ($\leq 8.5\%$, $\geq 8.6\%$), and baseline insulin use (no, yes).

We will conduct dose-response analyses to examine whether 12-month A1C differs based on the total value of incentives redeemed, a continuous variable, in the first 6 months for the mid-intervention analysis, and in the full 12-months for the post-intervention analysis.

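### Total dollars redeemed, the dose in the A1C and food insecurity dose-response analyses, mixes use of the incentive with household size, which is not a listed covariate; as-treated rule 3 sorts by household size, not usage (minor)

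*SAP*

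**What the plan says.** **Incentive (SAP 3.2).** The weekly amount is CDN 10.50 per household member, set from the size reported at baseline. Earning is all-or-nothing: "points were only given to households that met or exceeded their threshold each week". Redemption is looser: "earned points carried over between weeks, did not expire, and could be redeemed for anything in-store", in CDN 10 steps.

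**Dose (SAP 7.4 and 7.6).** Both dose-response analyses use the "total value of incentives redeemed, a continuous variable, in the first 6 months for the mid-intervention analysis", and the 12-month total for the post-intervention analysis. The value is not scaled to what the household could have received.

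**Covariates.** No separate list is given for the dose-response models, so the outcome's own list is the natural reading of 7.2. For A1C it includes baseline A1C and number of children. For food insecurity it includes baseline severity, number of children, marital status and income. Neither names household size, although 4.5 records "marital status, household size and composition" at baseline. Household composition is a covariate for other outcomes in 7.7 and 7.9.

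**Usage elsewhere.** SAP 5.4.1 states: "Incentive usage will be assessed as a count of the number of weeks participants earned the incentive and/or redeemed the incentive". As-treated rule 1 in 7.2 works by "using pre-specified cut points based on percentage of incentives redeemed", and rule 2 by weeks earned. Rule 3 sits under the same usage lead-in but compares single-person households with all larger ones.

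**The concern.** A dose-response analysis in the primary manuscript will be read as evidence on whether using the incentive more goes with better A1C. Raw dollars answer that only loosely, because two households using the incentive in every week can differ several-fold in dose through size alone. Two things could follow:

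- **Dilution.** If the effect runs through weeks of use, dollars are a noisy proxy. A flat slope could be misread as no effect of use.
- **Confounding.** If household size is related to the outcome given the other covariates, part of any slope belongs to size. This is plausible for food insecurity, where the item set depends on children at home ("Adults with no children living in the home completed the 10 questions for adults only"), although number of children is adjusted for. For A1C it is an assumption.

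Rule 3 raises a labelling problem: household size is fixed at baseline and says nothing about what was earned or redeemed.

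**Working it through.** **1. The plan's own example.** Weekly amount = 10.50 × size. For two people, 10.50 × 2 = 21, as in SAP 3.2.

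**2. Maximum dose** = 10.50 × size × weeks, leaving out the preloaded week.

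| Size | 26 weeks | 52 weeks |
|---|---|---|
| 1 | 273 | 546 |
| 2 | 546 | 1,092 |
| 4 | 1,092 | 2,184 |

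546/1,092 = 0.50 and 546/2,184 = 0.25, so 546 dollars is full, half or quarter use depending on size.

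**3. Assumptions.** The SAP gives no household mix or uptake, so 36 scenarios were simulated:

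- three mixes of sizes 1 to 6 (mean size 2.1 to 3.1);
- four uptake distributions (mean use 50 to 80% of weeks), unrelated to size;
- three adult/child splits: a partner then children; the same with half lone parents; each extra member a child with probability 0.4.

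Dollars = 10.50 × size × weeks.

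**4. How well dollars measure use.**

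- Household size explains 30 to 92% of the variance in dollars if everything earned is redeemed, and 26 to 85% if on average 67 to 80% is redeemed in 10-dollar steps.
- Given number of children, dollars share 11 to 79% (median 58%) of their variance with weeks earned. With household size added, 71 to 80%.

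**5. Power.** Suppose the true effect runs through weeks and a weeks model has 80% power. The expected test statistic is 1.96 + 0.84 = 2.80. With a proxy sharing a fraction r² of the variance it is 2.80 × √r² (normal approximation).

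- Median with children adjusted: 2.80 × √0.58 = 2.13; power Φ(2.13 − 1.96) = Φ(0.17) ≈ 57%. Over all scenarios, 16 to 70%.
- With household size added: 2.80 × √0.71 = 2.36 gives about 65%, and 2.80 × √0.80 = 2.50 gives about 71%; median about 68%.

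**6. False-positive bias, A1C.** No effect of use; assumed +0.10 A1C points per member at baseline and 12 months; SD 1.4; correlation 0.5, 0.6 or 0.7; adjusted for baseline A1C and children; 299 × 0.7 = 209 FoodRx participants.

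| Correlation | Largest slope per 1,000 dollars | Largest rejection | Median rejection |
|---|---|---|---|
| 0.5 | 0.096 | 9.6% | 5.2% |
| 0.6 | 0.077 | 8.4% | 5.2% |
| 0.7 | 0.057 | 7.4% | 5.1% |

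Median slopes are 0.02 to 0.04. At +0.05 per member the largest slope is about 0.05, with 6% rejection. With household size added, the slope is zero and rejection 5%.

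**7. False-positive bias, food insecurity.** No effect of use; assumed odds ratio 1.2 per member; proportional-odds model adjusted for baseline severity, children and a partner. There is no bias if the only other adult is a partner. With other adults at home, the false odds ratio per 1,000 dollars is 1.03 to 1.17 (median 1.08), with rejection 5 to 8%. Adding household size brings it to 0.99 to 1.02, with rejection 5%.

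**The case against.** - **The bias is close to nothing.** This stands. A median A1C slope of 0.02 to 0.04 per 1,000 dollars is 4 to 8% of the 0.5-point difference the SAP calls meaningful (0.02/0.5 and 0.04/0.5). The SAP does not say whether the comparison arm is dropped. With both arms (2 × 209 = 418) and a group term, the median slope is 0.011 and median rejection 5.1%.
- **Uptake may fall with household size**, since the threshold rises with it. This also stands. If the log-odds of earning fall by 0.25 or 0.5 per member (assumed), household size explains 20 to 82% or 11 to 63% of the variance in dollars.
- **Dollars delivered is a legitimate programme question, and 7.2 already has percentage redeemed and weeks earned.** Largely true, and a reason to keep dollars and give this low priority. But 7.2 uses those measures to classify people in as-treated analyses; neither is the dose in the continuous models of 7.4 and 7.6.
- **Weeks are not clearly better.** Correct for weeks redeemed: points carry over, so one shopping trip may spend months of value.
- **Adjustment removes the bias by construction**, because size is the only confounder simulated. True; self-selected uptake remains, as in any such analysis.
- **Rule 3 states openly what it compares.** It does, which limits the harm, but the usage label is still wrong.

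A reader might infer that the dollar analyses are seriously biased, or that the primary result is in doubt. The documents support neither. They give no link between household size and A1C, the computed bias is near nominal in most scenarios, and the primary test is the randomized group contrast.

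**Conclusion.** The point holds as a minor one. From the text alone, the ceiling of the dollar dose is proportional to baseline household size, neither parent covariate list names household size, and rule 3 does not classify anyone by usage.

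The main consequence is imprecision, not bias: median power of about 57% where a weeks model would have 80%, recovering to about 68% once household size is added. These figures rest on the assumed mixes and uptake and on an effect that runs through weeks of use; if the effect truly ran through dollars, dollars would be the right scale. False-positive rejection is about 5% at the median and at most about 10%, and needs an association between household size and the outcome that the SAP does not document. Only supportive analyses are touched.

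**What to change.** 1. In 7.4 and 7.6, list the dose-response covariates and include baseline household size.
2. Report dose also as value redeemed divided by the household's own maximum, 10.50 × size × weeks in the period (273 per member for 26 weeks, 546 for 52). Treat the preloaded week the same way in numerator and denominator.
3. Total dollars may stay if household size is adjusted for. If weeks are used, specify weeks earned, not weeks redeemed.
4. In 7.2, relabel rule 3 as a household-size (incentive-level) subgroup analysis using the randomized contrast within each size group, or delete it.

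The cost is SAP wording and one derived variable. Household size was collected at baseline, and a percentage redeemed is already planned for rule 1.

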5.2 Secondary Outcomes

5.2.1 Blood Glucose Levels

Glycemic control will also be assessed by 1) examining A1C levels as a continuous outcome at 6- and 18-months* to assess effectiveness of the intervention at midpoint and 6 months after cessation, 2) calculating the proportion of participants with elevated A1C as a binary outcome (A1C \geq 8.5%), and 3) examining fructosamine levels at 6- and 12-months as a continuous outcome as A1C can be unreliable for some participants⁵³⁻⁵⁵ and fructosamine is more sensitive to acute changes.⁵⁶

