18-month A1C We will assess group differences in 18-month A1C (i.e., 6-months post-intervention) as a continuous outcome using mixed-effects linear regression. Models will be adjusted for baseline A1C, and additional blocking variables (gender, recruitment location). To improve the precision of effect estimates, models will also be adjusted for age, race/ethnicity, educational attainment, number of children living in the home, and diabetes duration. Models will also include group (FoodRx vs comparison), and baseline A1C data source (study measured vs administrative health data) indicator variables. We will include random intercepts for participants (participant study ID) to account for within-subject correlation due to repeated measures, and for primary care clinics (clinic study ID) to account for clustering of participants within clinics.

In addition to per-protocol and as-treated analyses, we will conduct sensitivity analyses for 18-month A1C to examine 1) the impact of excluding A1C values obtained from administrative health data, 2) if findings differ when models include all participants regardless of A1C source, and a collection timing indicator variable (time since baseline, deviation from 18-month data collection timepoint), 3) the impact of using multiple imputation for missing data rather than full information maximum likelihood, 4) the impact of adjusting for changes in medication/insulin type between baseline and 6-months post-intervention follow-up, and 5) the impact of including the first measure of baseline A1C collected before the trial restart.

Elevated A1C We will assess group differences in elevated A1C as a binary outcome using mixed-effects logistic regression (odds ratios). Models will be adjusted for baseline A1C, and additional blocking variables (gender, recruitment location). To improve the precision of effect estimates, models will also be adjusted for age, race/ethnicity, educational attainment, number of children living in the home, and diabetes duration. Models will also include group (FoodRx vs comparison), and baseline A1C data source (study measured vs administrative health data) indicator variables. We will include random intercepts for participants (participant study ID) and primary care clinics (clinic study ID) to account for clustering of participants within clinics.

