In addition to per-protocol and as-treated analyses, we will conduct sensitivity analyses for elevated A1C to examine 1) the impact of excluding A1C values obtained from administrative health data, 2) if findings differ when models include all participants regardless of A1C source, and a collection timing indicator variable (time since baseline, deviation from 18-month data collection timepoint), 3) the impact of using multiple imputation for missing data rather than full information maximum likelihood, 4) the impact of adjusting for changes in medication/insulin type between baseline and 6-months post-intervention follow-up, and 5) the impact of including the first measure of baseline A1C collected before the trial restart.

Fructosamine We will assess group differences in fructosamine as a continuous outcome using mixed-effects linear regression at 6- and 12-months. Models will be adjusted for baseline fructosamine, and blocking variables (baseline A1C, gender, recruitment location). To improve the precision of effect estimates, models will also be adjusted for age, race/ethnicity, educational attainment, number of children living in the home, and diabetes duration. Additionally, all models will include baseline A1C data source (study measured vs administrative health data), and group (FoodRx vs comparison). We will include random intercepts for participants (participant study ID) to account for within-subject correlation due to repeated measures, and for primary care clinics (clinic study ID) to account for clustering of participants within clinics.

In addition to per-protocol and as-treated analyses, we will conduct sensitivity analyses for fructosamine to examine 1) the impact of excluding A1C values obtained from administrative health data, 2) if findings differ when models include all participants regardless of A1C source, and a collection timing indicator variable (time since baseline, deviation from 18-month data collection timepoint), 3) the impact of using multiple imputation for missing data rather than full information maximum likelihood, 4) the impact of adjusting for changes in medication/insulin type between baseline and 6-months post-intervention follow-up, and 5) the impact of including the first measure of baseline A1C collected before the trial restart.

Clinical Health Markers, Secondary Outcomes

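### Fructosamine, analysed at 6 and 12 months, is given sensitivity analyses timed to month 18, so item 4 adjusts it for medication changes made after it was measured

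*SAP*

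**What the plan says.** SAP section 5.2.1 lists, among the secondary glycaemic outcomes, "examining fructosamine levels at 6- and 12-months as a continuous outcome". Section 7.4 repeats this for the model: "We will assess group differences in fructosamine as a continuous outcome using mixed-effects linear regression at 6- and 12-months". Neither place plans an 18-month fructosamine analysis, and section 3.3 describes participant data collection at baseline, 6 and 12 months.

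The fructosamine paragraph in section 7.4 then gives five sensitivity analyses. The list begins "sensitivity analyses for fructosamine to examine 1) the impact of excluding A1C values obtained from administrative health data". Item 2 brings in a collection-timing variable that includes "deviation from 18-month data collection timepoint". Item 4 is "the impact of adjusting for changes in medication/insulin type between baseline and 6-months post-intervention follow-up". The SAP fixes what that follow-up means when it introduces "18-month A1C (i.e., 6-months post-intervention".

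The elevated A1C paragraph carries the same five items with the same month-18 wording. No time point for elevated A1C appears in section 5.2.1 or in its own paragraph. The opening of section 7.4 allows secondary outcomes at 6, 12 and/or 18 months.

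**The concern.** The fructosamine list matches the 18-month A1C list apart from the outcome name, and two of its elements do not fit an outcome measured at 6 and 12 months.

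Item 4 matters more. Section 4.3 says providers remained free to adjust medication to improve glycaemia during the trial. A medication change after the fructosamine sample may therefore be a consequence of the glycaemia that the sample measured. Entering it as a covariate conditions the outcome on something downstream of itself. If high glycaemia prompts intensification, the covariate would tend to absorb part of any real group difference, and the adjusted estimate would not answer a clear question.

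Item 2 measures timing deviation from a visit at which fructosamine is not analysed.

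An analyst holding this text must either run an ill-timed analysis or depart from the plan without a stated basis.

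**Working it through.** The plan gives no calculated figure on this point to reproduce. The check compares the lists in section 7.4 and works out the timeline.

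**Inputs**
- Fructosamine visits: months 6 and 12 (sections 5.2.1 and 7.4).
- Post-intervention: month 12 (section 3.3).
- Six months post-intervention: 12 + 6 = month 18, as the 18-month A1C paragraph confirms.

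**Lists in section 7.4 side by side**

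| Outcome | Outcome month(s) | Timing reference, item 2 | Medication window, item 4 | Matched? |
|---|---|---|---|---|
| 6-month A1C | 6 | 6 | 0 to 6 | yes |
| 12-month A1C (primary) | 12 | 12 | 0 to 12 | yes |
| 18-month A1C | 18 | 18 | 0 to 18 | yes |
| Fructosamine | 6 and 12 | 18 | 0 to 18 | no |
| Elevated A1C | not stated | 18 | 0 to 18 | cannot be judged |

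The SAP's own convention is that both elements end at the outcome's visit. Fructosamine is the only outcome with stated visits that departs from it.

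**Item 4: part of the window after the outcome** (end of window minus outcome month)
- 6-month fructosamine: 18 − 6 = 12 months; 12/18 = 67% of the window.
- 12-month fructosamine: 18 − 12 = 6 months; 6/18 = 33% of the window.
- With the window ending at the outcome's own visit: 6 − 6 = 0 and 12 − 12 = 0 months.

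**Item 2: effect of the wrong reference.** Let t be months since baseline. A signed deviation from month 18 is t − 18 = (t − 12) − 6 for the 12-month visit and t − 18 = (t − 6) − 12 for the 6-month visit. Each is the correct deviation shifted by a constant, so a linear term would lose little if the model also has a visit term. An absolute deviation would change meaning. For illustration, samples at months 11 and 13 are both 1 month from month 12, but 7 and 5 months from month 18. The SAP does not say which form is intended.

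**Items 1 and 2: A1C source.** Section 5.1 states the fallback to medical records or administrative data for A1C only, so excluding administrative A1C values removes no fructosamine outcome value. However, the fructosamine model adjusts for baseline A1C and includes an indicator for its source. These items can therefore act on that covariate, as can item 5, which concerns the baseline A1C taken before the restart.

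**The case against.** Much can be said on the other side.

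- **The A1C-source items have a possible function.** A reader might infer that items 1 and 2 are misplaced because A1C is not the outcome, and should be deleted. The documents do not support that. Baseline A1C and its data source are in the fructosamine model, so item 1 and the all-sources part of item 2 can be read as checks on that covariate. Only the wording is unclear. For the same reason a claim that most of the list fails to fit would be too strong: the firm defects are the deviation reference in item 2 and the window in item 4.
- **Elevated A1C is not shown to have the timing error.** A reader might infer the same defect from the identical text. But section 7.4 allows 18 months for secondary outcomes, and at 18 months the text would be correct. What is established is a missing time point.
- **The consequence is limited.** Section 5.2.1 includes fructosamine partly because A1C can be unreliable for some participants. It is tempting to conclude that this back-up evidence would mislead. That role belongs to the main fructosamine model, which is correctly timed. Section 6.5 also treats secondary outcomes as exploratory.
- **Medication changes up to the same visit are also post-randomisation.** They can respond to interim glycaemia, and section 5.2.2 makes medication need an outcome in its own right. Matching the window removes only the post-outcome part. It does not make the adjusted estimate a total effect of the programme.

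All four points stand. None of them rescues the month-18 reference or the month-18 window for fructosamine.

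**Conclusion.** Wrong as written, and minor. For fructosamine, item 4 adjusts for medication changes extending 12 months past the 6-month outcome and 6 months past the 12-month outcome, and item 2 uses a reference that matches neither visit. The conclusion assumes that six months post-intervention means month 18 throughout section 7.4, as its 18-month A1C paragraph states.

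The figures are lengths of calendar time. The documents give no rate of late medication change, so the bias cannot be sized. The effect is confined to sensitivity analyses of secondary outcomes: the main fructosamine model, the primary 12-month A1C analysis with its matched list, and the sample size do not change. For elevated A1C the finding is only that the time point is unstated. The month-18 text would be wrong there if the outcome were analysed at 6 or 12 months.

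**What to change.** In SAP section 7.4:

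1. **Fructosamine, item 2.** Define timing deviation from the 6-month visit for the 6-month outcome and from the 12-month visit for the 12-month outcome.
2. **Fructosamine, item 4.** End the medication-change window at the same visit as the outcome, as the 6- and 12-month A1C lists already do.
3. **Fructosamine, items 1 and 2.** State that they concern the source of the baseline A1C covariate.
4. **Elevated A1C.** Name the analysis time point or points, and give each its own timing reference and medication window.

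It would also help to note that the medication-adjusted results condition on post-randomisation changes and should be read accordingly.

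The cost is SAP wording only, best settled before these analyses are run. No new data or change in sample size is needed.
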